10. SAFETY

Safety analyses will be performed for the safety analysis population.

10.1 Adverse Events

Adverse events will be classified by system organ class and preferred term using the Medical Dictionary for Regulatory Activities (MedDRA) Version 18.0 or higher. Unless otherwise specified, treatment-emergent adverse events (TEAEs), that is any AEs reported after initiation of treatment with S-888711 or placebo, will be used for the analyses of safety.

The number of patients who experienced at least 1 TEAE and corresponding incidence will be calculated by treatment group. The incidence of TEAEs will be reported along with 95% CIs, which will be calculated with Clopper-Pearson method. The number of TEAEs, counted by cases reported, will also be presented. Death, treatment-emergent serious adverse events (SAEs), TEAEs leading to withdrawal of the study drug, and treatment-related AEs will be summarized in the same manner as the overall summary of TEAEs. The definitions of death, treatment-emergent SAEs, TEAEs leading to withdrawal of the study drug, and treatment-related AEs are shown below.

Term	Definition
Death	TEAEs with “Fatal” in terms of outcome.
Treatment-emergent SAEs	TEAEs with “Serious” in terms of seriousness
TEAEs leading to withdrawal of the study drug	TEAEs with “Drug withdrawn” in terms of the action taken for study drug.
Treatment-related AEs	TEAEs with “Related” in terms of the causal relationship with study drug.

The number of patients who experienced TEAEs and corresponding incidence will be calculated by system organ class (SOC) and preferred term (PT) for each treatment group. In the calculation, a patient who experienced a particular TEAE more than once will be counted only once within a SOC and PT. Treatment-emergent SAEs, TEAEs leading to withdrawal of the study drug, and treatment-related AEs will be summarized in a similar manner.

The number of patients who experienced TEAEs in each category of severity and outcome will be counted by SOC and PT for each treatment group, and the corresponding incidence in each category will be calculated. For patients who experienced a particular TEAE more than once in different categories, the patient will be counted only once using the highest priority category shown in Table 3. Treatment-related AEs will be summarized in a similar manner.

Table 3 Priority of Categories

Priority	Category	
	Severity	Outcome
1	Severe	Fatal
2	Moderate	Recovered/resolved with sequelae
3	Mild	Not recovered/not resolved
4		Recovering/resolving
5		Recovered/resolved
6		Unknown

For the patients who underwent invasive procedure in safety analysis population, the summary of TEAEs before and after the primary invasive procedure will be presented by SOC and PT for each treatment group. In the calculation of the number of patients and corresponding incidence, a patient who experienced a particular TEAE more than once will be counted only once. Treatment-related AEs will be summarized in a similar manner.

The number of patients who experienced bleeding-related TEAEs and corresponding incidence will be calculated by SOC and PT for each treatment group. A patient who experienced a particular TEAE more than once will be counted only once within a SOC and PT. Bleeding-related TEAEs will be defined as TEAEs which were classified as “haemorrhage terms (except laboratory terms)” using Standard MedDRA Queries (SMQ).

10.2 Adverse Events of Special Interest

Thrombotic/thromboembolic events will be considered as adverse events of special interest in this study. The definition of thrombotic/thromboembolic TEAEs is described as TEAEs which are classified as follows using the SMQ:

- “embolic and thrombotic events, arterial”
- “embolic and thrombotic events, venous”
- “embolic and thrombotic events, vessel type unspecified and mixed arterial and venous”.

The number of patients who experienced thrombotic/thromboembolic TEAEs and corresponding incidence will be calculated by SOC and PT for each treatment group. A patient who experienced a particular TEAE more than once will be counted only once within a SOC and PT.

10.3 WHO Bleeding Scale

For each WHO Bleeding Scale, the number and proportion of patients will be calculated by treatment group at each scheduled time point (Days 1, 8, 35, after the primary invasive procedure and last observation).

10.4 Vital Signs

For systolic blood pressure, diastolic blood pressure, and pulse rate, summary statistics of observations and their changes from baseline will be calculated at each scheduled time point (Days 1, 5, 8, 10, 12, 14, 21, 28, 35 and last observation) by treatment group.

10.5 Electrocardiography

The number and proportion of patients with an abnormal ECG finding will be calculated by treatment group at Day 35 and last observation.

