7.7.6 Electrocardiography

Electrocardiography (ECG) will be performed during the Screening period and on Day 35 (or at drug withdrawal and/or early termination of assessment, if applicable).

All ECG traces will be evaluated by the investigator or designee and categorised as normal or abnormal. The date of the ECG and any abnormality observed should be recorded on the CRF. Any abnormal traces will be reviewed by the investigator or designee for clinical significance (see also Section 7.8.9), with any clinically significant findings recorded as an AE on the CRF.

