8.11.4 Laboratory Tests

Summary statistics for laboratory tests, measured after randomisation, and their changes

from baseline will be calculated at each scheduled time point by treatment group. Baseline will be the value obtained on Day 1 (before initiation of study medication). If the value on Day 1 is missing and the value obtained before randomisation was obtained within 7 days of initiation of study medication, that value can be used as a baseline measurement.

8.11.5 **Electrocardiogram**

The number and proportion of patients with an abnormal ECG finding will be calculated at each scheduled time point.

8.11.6 **Portal Vein Thrombosis**

The number and proportion of patients who experienced portal vein thrombosis will be counted.

8.11.7 **Portal Blood Flow**

Summary statistics by category for the direction of portal blood flow (ie, hepatofugal, hepatopetal, stasis) will be counted for patients who underwent Doppler ultrasonography at each scheduled time point.

8.12 **Pharmacokinetic Analysis**

Plasma S-888711 concentrations will be listed by nominal sampling time and sampling design group (intensive PK sampling or sparse PK sampling). Plasma S-888711 concentrations for patients who completed at least 5 days of study drug administration will be summarised by nominal sampling time and sampling design group. Summary statistics will include the number of non-missing observations (N), arithmetic mean (Mean), SD, and coefficient of variation (CV%, calculated by $SD/Mean \times 100$), geometric mean and coefficient of variation for geometric mean (CV% Geometric Mean), and median, minimum, and maximum values at each sampling time. The CV% Geometric Mean will be calculated according to a formula $CV\% \text{ Geometric Mean} = [\exp(sd^2)-1]^{1/2} \times 100$, where sd is the standard deviation for natural logarithm (ln)-transformed data. Time course profiles for plasma concentration data will be presented graphically. Based on plasma concentration data on Days 5 and 6 and using non-compartmental methods, the following PK parameters will be calculated, whenever possible, for each patient who completed at least 5 days of study drug administration in the intensive PK sampling group:

C_{\max} (ng/mL): Maximum plasma concentration

T_{\max} (hr): Time to C_{\max}

$AUC_{0-\tau}$ (ng·hr/mL): AUC over the dosing interval τ (ie, 24 hours), calculated by the trapezoidal method (Linear Up/Log Down Trapezoidal Method)

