2. STUDY OVERVIEW

This is a phase 3, multinational, randomized, double-blind, placebo-controlled study to assess the safety and efficacy of S-888711 for the treatment of thrombocytopenia in patients with CLD undergoing elective invasive procedures. The study consists of 3 periods:

[figure not shown]
- Screening period: up to 28 days prior to randomization
- Treatment period: up to 7 days (Days 1 to 7)
- Post-treatment period: through 28 days post-treatment

The maximum study duration for each patient will be 63 days. Potential patients who provide written informed consent will be screened for eligibility, and eligible patients will be randomized in a 1:1 ratio to either S-888711 3 mg once daily for up to 7 days or matched placebo control. The randomization will be stratified by primary invasive procedure (liver ablation/coagulation or other invasive procedures) and baseline platelet count ($< 35 \times 10^9/L$ or $\geq 35 \times 10^9/L$).

Patients will begin once daily treatment with assigned study medication on Day 1 after randomization and will receive study medication for up to 7 days. A platelet count will be performed on Days 5, 6, and 7 prior to administration of study medication. After the final dose of study medication, patients will continue the protocol-specified assessments and procedures in the Post-treatment period.

The planned invasive procedure will be performed in the Post-treatment period between Days 9 and 14. A platelet count will be performed on or after Day 8, but no more than 2 days prior to the elective invasive procedure in order to assess the need for a platelet transfusion before the planned elective procedure. A preoperative platelet transfusion must be performed if the platelet count is $< 50 \times 10^9/L$.

Study Schematic

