6.5.2 Baseline

The baseline value is defined as a value obtained on Day 1 before administration of the initial dose of study drug. If this value is missing, the most recent value obtained prior to Day 1 within the 7 preceding days will be used as the baseline value. Regarding body weight, height, and body mass index (BMI), the measurement at screening visit will be used as the baseline value.

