6.5.3 Last Observation

Last observation will refer to the last nonmissing observation after baseline which is within the analysis visit window and used in the analysis (see [Section 6.3](#)) or is within 7 days after the day of early termination of study assessment.

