13. CHANGES FROM PROTOCOL

- An analysis using the van Elteren is added in order to compare the duration of the increase in platelet count between S-888711 and placebo group for the ITT population (see [Section 9.2.3](#))
- Summary of significant TEAEs is removed because this event was not defined in the protocol.

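### SAP 10.5 drops the Screening ECG that the protocol would tabulate, so the ECG table mixes pre-existing with new abnormalities (minor, descriptive)

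*SAP*

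**What the plan says.** **Schedule.** Protocol 7.7.6 states: "Electrocardiography (ECG) will be performed during the Screening period and on Day 35", or at drug withdrawal or early termination where that applies. The Time and Events Schedule (Appendix 1) agrees. It shows no Day 1 ECG. Each tracing is "categorised as normal or abnormal", so the result is binary.

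**Protocol analysis (8.11.5).** "The number and proportion of patients with an abnormal ECG finding will be calculated at each scheduled time point".

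**SAP analysis (10.5).** The output is patients with an "abnormal ECG finding will be calculated by treatment group at Day 35 and last observation". There is no Screening row, no shift table and no count restricted to patients who were normal at Screening.

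**SAP definitions.** Section 6.5.3: "Last observation will refer to the last nonmissing observation after baseline", subject to window rules. Section 6.5.2 takes the pre-dose Day 1 value as baseline; if that is missing, "the most recent value obtained prior to Day 1 within the 7 preceding days will be used as the baseline value". Section 2 gives the "Screening period: up to 28 days prior to randomization".

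**Declared changes (SAP 13).** Two are listed: the added van Elteren analysis, and "Summary of significant TEAEs is removed because this event was not defined in the protocol". The ECG table is not mentioned.

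**The concern.** With a binary result and no Day 1 tracing, the Screening ECG is the only scheduled information on a patient's state before dosing. Once it leaves the summary, the Day 35 and last-observation counts combine patients who arrived with an abnormal ECG and patients who developed one. No eligibility criterion requires a normal ECG. Exclusion criterion 8 removes some cardiac conditions, such as atrial fibrillation, but not abnormal tracings in general, so pre-existing abnormalities can enter the trial.

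At stake is the readability of one safety table. A difference between arms could reflect chance imbalance at entry, and a small excess of new abnormalities could be lost among old ones. There is also a traceability gap: a protocol-specified summary was narrowed without an entry in the list of changes.

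**Working it through.** The plan states no ECG figure to reproduce. The check is mainly a comparison of text, with a short illustration.

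**1. Does the protocol's wording include Screening?** Protocol 8.11.3 and 8.11.4 restrict vital-sign and laboratory summaries to values taken after randomisation. Section 8.11.5 carries no such restriction. Without Screening, its scheduled time points would reduce to Day 35 plus withdrawal or early termination. The natural reading includes Screening.

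**2. Could the SAP's last observation stand in for Screening?** No. SAP 6.5.3 makes it post-baseline.

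**3. Is the omission in line with the other SAP safety tables?** No.

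| SAP table | Pre-treatment reference |
|---|---|
| WHO Bleeding Scale (10.3) | Day 1 |
| Vital signs (10.4) | Day 1 and change from baseline |
| ECG (10.5) | none |
| Laboratory tests (10.6) | Day 1 and change from baseline |
| Portal vein thrombosis, portal blood flow (10.7) | Screening |

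The portal assessments are the closest parallel: they too have no Day 1 assessment, and there the SAP keeps Screening.

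**4. Does SAP 6.5.2 supply an ECG baseline?** Not reliably. Screening may run to 28 days before randomisation and the fallback accepts only the 7 days before Day 1. A Screening ECG may or may not qualify.

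**5. How much can the SAP table conceal?** The documents give no ECG abnormality rate, so these inputs are assumed: 100 patients per arm (the planned size), a share *p* abnormal at Screening and none resolving, and new abnormality in 3% of those normal at Screening.

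Expected abnormal at Day 35 per 100 = 100 × [*p* + (1 − *p*) × 0.03]; new cases = 100 × (1 − *p*) × 0.03.

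| *p* | Abnormal at Day 35 | Of which new |
|---|---|---|
| 0% | 3.0 | 3.0 |
| 10% | 12.7 | 2.7 |
| 20% | 22.4 | 2.4 |
| 30% | 32.1 | 2.1 |
| 40% | 41.8 | 1.8 |

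The Day 35 count follows the entry prevalence and says little about new cases.

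**6. Would restoring the row be enough?** Take *d* = 30 abnormal at Day 35 among *n* = 100, now allowing resolution. With *s* abnormal at Screening, new cases lie between max(0, *d* − *s*) and min(*d*, *n* − *s*):

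- no Screening count: 0 to 30
- *s* = 10: 20 to 30
- *s* = 20: 10 to 30
- *s* = 30: 0 to 30

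The row helps, but it gives only marginal counts. Only the within-patient cross-classification fixes the number of new cases.

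**7. Noise from chance imbalance at entry.** The 95% half-width for the difference between arms in pre-existing prevalence is 1.96 × √[2*p*(1 − *p*)/100]. For assumed *p* of 20%, 30% and 40% this is 11.1, 12.7 and 13.6 percentage points.

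**The case against.** The strongest reply is that new ECG findings have another route into the report. Protocol 7.7.6 has abnormal tracings reviewed for clinical significance, and significant ones are recorded as adverse events. Protocol 7.8.1 counts abnormal ECG findings among adverse events and takes worsening from Screening as the reference. SAP 10.1 tabulates treatment-emergent events by arm, by system organ class and preferred term, and SAP 6.1 provides patient listings. This stands, and it narrows the point to new abnormalities judged not clinically significant. Listings hold those results, but they give no by-arm count.

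Three stronger readings are tempting, and the documents support none of them:

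- **That the between-arm ECG comparison is biased.** Allocation is randomised 1:1, so pre-existing abnormality is balanced in expectation. What remains is dilution and noise.
- **That the Screening ECG would as a rule fail the baseline definition.** The documents do not say when within Screening the ECG is taken. It may fall outside the 7 days, and no more than that can be said. SAP 10.5 in any case uses no baseline ECG.
- **That a loss of power can be quoted.** No ECG hypothesis test is planned, and the documents give neither a background rate nor an effect size. Any detection rate would rest on invented inputs.

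It is also fair to say that protocol 8.11.5 asks only for counts at time points. The shift table goes beyond the protocol and is recommended as a cheap improvement; its absence is not a departure from the protocol.

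**Conclusion.** The point holds as a minor one. SAP 10.5 omits the only scheduled pre-dose ECG from a summary that the protocol specifies at each scheduled time point, and SAP 13 does not declare it. The resulting table cannot distinguish old from new abnormalities. The loss is a by-arm summary of new ECG abnormalities not judged clinically significant. It would be wrong to infer that the trial has no means of seeing new ECG abnormalities, since clinically significant ones reach the adverse-event tables.

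The textual conclusion rests on reading the protocol's scheduled time points as including Screening, which the contrast with 8.11.3 and 8.11.4 and the handling in SAP 10.7 both support. The numerical illustrations rest on assumed prevalences and a 3% new-abnormality rate; they show the mechanism and do not predict the trial's results. This is a descriptive safety table, and neither the primary analysis nor the sequential tests depend on it.

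**What to change.** In SAP 10.5:

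1. Restore the Screening row, by treatment group.
2. Add a normal/abnormal shift table by arm, from Screening to Day 35 and from Screening to last observation, with missing tracings shown as their own category.
3. Name the Screening ECG as the ECG baseline, as an exception to SAP 6.5.2, so that an ECG last observation also has a defined baseline to follow.

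If the sponsor prefers to keep the table as it is, the omission should be listed and justified in SAP 13.

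The cost is one row, one small table and a sentence or two of SAP text. Protocol 7.7.6 already puts ECG dates and abnormalities on the CRF, so no new data or visits are needed.

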10.6 Laboratory Tests

For laboratory tests listed in [Table 4](#), summary statistics of observations and their changes from baseline will be calculated at each scheduled time point (Days 1, 8, 14, 35 and last observation) by treatment group.

Table 4 List of Laboratory Tests

Test	Items Evaluated
Haematology (except for platelet count)	Red blood cell count, white blood cell count, haemoglobin, and haematocrit
Blood Chemistry	Aspartate aminotransferase (AST), alanine aminotransferase (ALT), lactate dehydrogenase, gamma glutamyl transferase, alkaline phosphatase, total bilirubin, bilirubin direct, indirect bilirubin, total protein, albumin, blood urea nitrogen, serum creatinine, sodium, potassium, chloride, and calcium
Blood Coagulation/Fibrinolysis Assay	Prothrombin time-international normalized ratio (PT-INR), activated partial thromboplastin time

Individual clinically significant abnormalities (ICSA) will be summarized based on criteria which are determined by reference to Common Terminology Criteria for Adverse Events (CTCAE) Version 4.0 (see [Appendix 4](#)). For each CTCAE term shown in Appendix 4, the number and proportion of patients with a laboratory test result classified as grade 2 or more will be calculated at each scheduled time point (Days 1, 8, 14, 35) by treatment group. In addition, the number and proportion of patients with a laboratory test result classified as grade 2 or more at least once after the initiation of study drug will be calculated. For the term “hyponatremia”, the number and proportion of patients with a laboratory test result classified as grade 3 or more will be summarized because the term doesn’t have criteria for grade 2. The upper limit of normal range for PT-INR is regarded as 1 if it will not be specified by the central laboratory.

The number and proportion of patients who met the following criteria for liver function abnormalities will be calculated at each scheduled time point (Days 1, 8, 14, 35) by treatment group. The number and proportion of patients with liver function abnormalities after the initiation of study drug will also be calculated.

- AST or ALT $\geq 3 \times$ upper limit of normal (ULN) and total bilirubin $\geq 2 \times$ ULN
- AST or ALT $\geq 3 \times$ ULN and PT-INR ≥ 1.5
- AST/ALT ≥ 3

10.7 Portal Vein Thrombosis and Portal Blood Flow

For the patients who underwent diagnostic imaging in safety analysis population, the number and proportion of patients who experienced portal vein thrombosis at screening and after the primary invasive procedure will be calculated by treatment group. The patients who underwent an invasive procedure more than once will be regarded as having portal vein thrombosis if they experienced it at least once after the primary invasive procedure. If a patient received an invasive procedure and underwent assessment of portal vein thrombosis on the same day, the assessment will be considered as being after invasive procedure (see [Section 6.3](#)).

For the patients who underwent Doppler ultrasonography in safety analysis population, summary statistics by category for the direction of portal blood flow (i.e., hepatofugal, hepatopetal, stasis) at screening and after the primary invasive procedure will be calculated by treatment group. If a patient received an invasive procedure and underwent Doppler ultrasonography on the same day, the assessment will be considered as being after invasive procedure (see [Section 6.3](#)).

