7.4 Invasive Procedures

The planned invasive procedure will be performed in the Post-treatment period between Days 9 and 14. The need for the invasive procedure will be reassessed in the event of the following:

- Platelet count $\geq 200 \times 10^9/L$
- Administration of an antithrombotic drug
- In the opinion of the investigator, the procedure is no longer in the patient's best because of an AE or other concern
- The patient requests cancellation of elective procedure after randomisation

If any of the above criteria are met and the elective procedure cannot be performed between Days 9 and 14, it may be performed up to Day 35 of the study. If a patient does not undergo a procedure, all relevant follow-up assessments should be performed and data should be collected up to Day 35. In case the invasive procedure performed between Days 9 and 14 needs to be repeated, the same procedure may be performed after Day 15 according to the discretion of the investigator.

Information on whether to perform the planned invasive procedure, details of the procedure performed (eg, percutaneous radiofrequency ablation [RFA]/microwave coagulation therapy [MCT], laparoscopic RFA/MCT, endoscopic variceal ligation [EVL], endoscopic injection sclerotherapy [EIS], TACE, TAE, or other), the date performed, the initiation time of the procedure, and whether the procedure was performed within the specified period will be recorded on the CRF. If the planned invasive procedure is not performed within the specified period or is not performed at all, the reason will be recorded on the CRF.

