7.7.2 Portal Vein Thrombosis

Portal vein thrombosis will be assessed by the investigator or designee using diagnostic imaging (ultrasonography, CT, or MRI) during the Screening period, and between 3 and 10 days after the planned invasive procedure* in the Post-treatment period (Days 12 to 21). For assessment in the Screening period, the investigation should be arranged as close to randomisation as possible. However, for patients in whom gastro-oesophageal varices are treated, portal vein thrombosis will be confirmed using imaging performed after the treatment.

The imaging date and method, and the presence or absence of portal vein thrombosis will be recorded on the CRF. The independent safety committee will assess portal vein thrombosis (see Section 9.8.2).

* Even if the planned invasive procedure is postponed. In addition, if any additional invasive procedures are performed, diagnostic imaging should also be performed before and after the additional procedure for post-assessment of the initial and additional procedures.

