6.3 Analysis Visit

Analysis visit windows are defined as shown in Table 1 to determine the analysis value for each study visit. Measurements collected outside of the visit window will be considered missing for that study visit. For all patients with multiple values within a visit window, the value obtained closest to the target study day will be used. In the case of multiple observations equidistant to the study visit date, the later one will be used, unless otherwise noted. Only for screening visit, the earliest one will be used for analysis if multiple values were obtained within 28 days prior to randomization.

In regard to “after the invasive procedure”, which is the analysis visit for WHO Bleeding Scale, Portal Vein Thrombosis, and Portal Blood Flow, the allowance is within 3 days to 10 days after the first invasive procedure. In the case of multiple observations equidistant to the study visit date, the earlier one will be used, unless otherwise noted.

Table 1 Analysis Visit Windows

Study Day for Analysis	Allowance
Screening	Within 28 days prior to randomization
Day 1 (Baseline)	Within 7 days before initiation of study medication
Days 5-7	± 0 day
Day 8	± 0 day
Day 10	± 1 day
Days 12 and 14	+1 day
Days 17 and 21	-1 day to +2 days
Day 28	± 2 days
Day 35	-2 day to +7 days

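### The portal vein thrombosis imaging table in SAP 10.7 has no post-dose place for patients without a procedure or for scans before it; add a row for any imaging after first dose

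*SAP*

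**What the plan says.** - **Protocol 8.11.6** gives the analysis in one sentence, with no condition on a procedure: "The number and proportion of patients who experienced portal vein thrombosis will be counted".
- **SAP 10.7** restricts the time points. It reports patients who "experienced portal vein thrombosis at screening and after the primary invasive procedure will be calculated by treatment group". The denominator is introduced with "For the patients who underwent diagnostic imaging in safety analysis population"; it does not say whether this means imaged at that time point or imaged at all.
- **SAP 6.3** defines the post-procedure visit: "the allowance is within 3 days to 10 days after the first invasive procedure". For analysis visits in general, "Measurements collected outside of the visit window will be considered missing for that study visit".
- **SAP 10.7** adds two rules. A patient with more than one procedure counts as a case if thrombosis is found at any time after the primary one. A scan on the day of the procedure is treated as after it. There is no rule for a patient with no procedure.
- **Protocol 7.7.2** schedules the imaging at screening and "between 3 and 10 days after the planned invasive procedure* in the Post-treatment period (Days 12 to 21"), with the footnote "Even if the planned invasive procedure is postponed".
- **Protocol 7.4** states that "The need for the invasive procedure will be reassessed in the event of the following" and lists a platelet count of at least 200 x 10^9/L, an antithrombotic drug, an adverse event or other investigator concern, and patient request. The procedure may then be done up to Day 35. A patient with no procedure stays in follow-up to Day 35.
- **SAP 13** lists two changes from the protocol. This is not one of them.

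**The concern.** Portal vein thrombosis is one of two events that protocol 7.8.8.1 singles out for particular attention, and SAP 10.7 is the only tabulation of the imaging scheduled to look for it. The post-dose part of that table depends on the patient having had the procedure. The events that prompt reassessment of the procedure include a very high platelet count and antithrombotic treatment, and protocol 6.2.1.3 allows the latter when thrombus is highly suspected. So whether a patient appears in the table may be related to the outcome that the table counts. Events are expected to be few, and one or two cases left out would change the reported proportion noticeably.

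**Working it through.** **1. Who has a place in the table.** Take SAP 10.7 and 6.3 together.

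| Dosed patient | Post-dose row in SAP 10.7 |
|---|---|
| Procedure done, scan 3 to 10 days later | Counted |
| Procedure done, thrombosis seen on a scan on an earlier day | That scan is not counted |
| No procedure, scan at follow-up, withdrawal or an unscheduled visit | No time point exists |

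The screening row cannot fill the gap. Exclusion criterion 10 bars patients with portal vein thrombosis on imaging within 28 days before randomisation, so that row describes eligibility and not treatment.

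**2. Whether such scans can exist.** Protocol 7.4 asks for all relevant follow-up to Day 35 when there is no procedure, without naming the imaging. The schedule in protocol Appendix 1 appears to include this imaging at withdrawal and unscheduled visits, but the table layout was broken in the text available, so I read it with caution. Its footnotes also limit the supply: patients stopped under the administration stopping criterion are exempt from the withdrawal assessments, and unscheduled visits include only what is necessary. The postponement footnote in protocol 7.7.2 can be read as keeping the scan at Days 12 to 21 when the procedure is delayed; such a scan could precede the procedure.

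**3. Whether the SAP expects patients without a procedure.** It does. They are failures in SAP 9.1, a subgroup category in SAP 9.1.1.1 and a sensitivity case in SAP 9.1.2.

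**4. What the SAP does elsewhere.** Sections 10.3 to 10.6 add a last observation, and 10.6 also counts patients with an abnormality at least once after starting study drug. Section 10.7 has neither.

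**5. Loss of denominator.** The plan's own safety figure (SAP 4.3) is at least 95% probability of seeing an event of 3% incidence with 100 per arm: 1 - 0.97^100 = 95.2%, which reproduces. The documents give no rate of patients without a procedure. Assuming 2, 5 or 10 per 100:

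- n = 98: 1 - 0.97^98 = 94.9%
- n = 95: 1 - 0.97^95 = 94.5%
- n = 90: 1 - 0.97^90 = 93.6%

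Fewer patients in the table is a small matter in itself.

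**6. Loss of cases.** Assume 100 dosed in an arm, 3 with portal vein thrombosis and 5 not operated. The any-time proportion is 3/100 = 3.0%. With k of the 3 cases among the non-operated, the table gives:

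| k | Denominator: imaged after the procedure, (3 - k)/95 | Denominator: ever imaged, (3 - k)/100 |
|---|---|---|
| 0 | 3.2% | 3.0% |
| 1 | 2.1% | 2.0% |
| 2 | 1.1% | 1.0% |
| 3 | 0% | 0% |

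Under the second denominator a non-operated case is counted as a non-case. All inputs to this table are assumed; it shows sensitivity and is not an estimate.

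**The case against.** The strongest reply is that thrombosis is analysed elsewhere. SAP 10.2 counts every thrombotic or thromboembolic treatment-emergent event by preferred term in all dosed patients, with or without a procedure. Protocol 8.11.2 names portal vein thrombosis among these events, protocol 7.8.1 makes abnormal diagnostic results adverse events, the Independent Safety Committee reviews them, and SAP 6.1 provides patient listings. This stands, and it limits the severity. What it leaves open is that SAP 10.2 depends on the finding being reported as an event and has no imaged denominator.

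It can also be said that SAP 10.7 simply tabulates the time points scheduled in protocol 7.7.2, and that a time-point summary need not equal an any-time incidence. That is fair: differing counts would not be a contradiction. They would need explaining, and the SAP gives no explanation.

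Three stronger readings are tempting and are not supported:

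- **That this is the key safety table and cases vanish from the safety analysis.** No section gives it that status, and SAP 10.2 covers all dosed patients.
- **That high counts or thrombosis cancel the procedure and so bias the table in favour of active drug.** The criteria in protocol 7.4 prompt reassessment and allow a procedure up to Day 35, after which most postponed patients can still be imaged. Thrombosis is not itself a listed criterion; it can act only through an adverse event or antithrombotic use. Patient request has no stated link to platelet response. No rate of patients without a procedure is given by arm.
- **That one missed case halves the rate**, taking the 2.1% (1/48) per arm in the Japanese phase 3 study. That figure covers all thrombotic events. The documents give no rate for portal vein thrombosis alone.

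**Conclusion.** The point holds as a gap in one descriptive safety table. As written, SAP 10.7 does not count post-dose portal vein thrombosis found in a patient without a procedure or on a scan before the procedure. This is narrower than protocol 8.11.6 and is not declared in SAP 13. The omission could be informative, because the events that prompt reassessment are plausibly related to thrombotic risk; its direction and size cannot be determined from the documents. In the assumed example the row moves between 0% and 3.2% against 3.0%, depending only on where three cases fall. The conclusion rests on applying SAP 6.3 as written and on some post-dose scans existing outside the post-procedure window. It does not mean that the main thrombosis analysis is lost, provided that such findings are reported as adverse events. Severity is minor to moderate.

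**What to change.** In SAP 10.7:

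1. Add a row for portal vein thrombosis on any imaging after first dose (scheduled, withdrawal or unscheduled) in all safety-population patients with post-dose imaging, whether or not a procedure took place.
2. Keep the after-procedure row.
3. State the denominator of each row.
4. Report by arm the number with no procedure and the number with no post-dose imaging.
5. Cross-refer to SAP 10.2, so that a difference between the two tables can be read.

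The cost is SAP wording and a little programming on data already collected; no new imaging is needed. The drawback is that unscheduled scans are driven by symptoms, so the any-imaging row mixes scheduled and prompted detection. That is the reason to keep the scheduled post-procedure row beside it.
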